#### **Study Methodology:**

Subjects will be provided with information about this research study by the following means: a member of the research team (IMG Nurse Practitioners) will discuss the research study during the patient's second pre-operative visit; study information will be uploaded to their MyChart portal; and flyers will be available in the IMG office (refer to appendix A: IMG office flyer). Interested patients will be able to fill out a brief form (refer to appendix B: Interested patient card) requesting to be contacted for further information, this form will be placed in a secure box at the reception desk or the patients can indicate interest by contacting one of the research team members. A member of the research team may need to access medical record information in order to confirm potential patient's phone number and or email address for further contact. A member of the research team will contact any interested patients and answer any questions regarding the research study. Consent will be obtained while the patient is in the peri-operative holding area on day of surgery by a member of the research team, excluding the IMG Nurse Practitioners. The research team member will determine if the patient is eligible for the study, discuss the study, answer any questions, and obtain consent (refer to appendix C: Consent). All members of the research team have completed Informed Consent Training. Once the consented post-operative bariatric patient complains of initial nausea on the Surgical Unit, the direct care nurse or research team member will ask the patient to rate their nausea level using a VAS on a 0-3 scale. Patients will be provided with either product A or B based on randomization scheme calculated by SAS (ver.9.4, Cary, NC). The patient will receive a one-time aromatherapy intervention. Nausea levels will be reassessed 5 minutes after the aromatherapy intervention. If the nausea level does not improve after the study drug intervention an antiemetic medication will be offered (refer to appendix D: Data Collection Form A).

On day of discharge a member of the research team will ask the patient the following questions regarding the Aromatherapy QueaseEASETM product (refer to appendix E: Data Collection Form B). The study will occur Monday through Thursday.

Did you use the QueaseEASE IM product?	Yes N	No	
If yes: How beneficial was the aromatherapy?	0 1 2 no benefit	3 4 5 very bene	eficial

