#### 3.3 Randomization

Upon enrollment in the trial, each subject will be randomized to one of two treatment groups: Product A (aromatherapy inhaler product), Product B (Placebo product: inhaler with distilled water). Each product will look the same. SAS will be used to generate the randomization table using random numbers to determine which treatment subject #1 will receive; subject #2 will receive, etc., resulting in a total of 90 subjects for each treatment group. The randomization scheme will be located in a secured location in the pharmacy department and access will be granted to Pharmacy and designated research team members.

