# 4 STATISTICAL CONSIDERATIONS/DATA ANALYSIS

# 4.1 Sample Size

To test the primary hypothesis that aromatherapy will lead to a decrease in post-operative nausea among patients undergoing laparoscopic/robotic sleeve gastrectomy, Roux-En-Y, and/or revisional bariatric surgery we will use a Pearson Chi-Square test for proportion difference. Assuming an expected incidence of nausea among controls of 80%, an alpha level of 5 percent, and a 1:1 treatment to control group ratio, we anticipate 90 subjects per group (n= 180 total) provides at least 80% power will to detect a statistically significant 20% reduction in the incidence of nausea among aromatherapy patients. The randomization scheme was calculated with SAS (ver.9.4., Cary, NC) using a two-group (treatment vs. placebo), simple randomization block (n=15) design. The total randomization scheme was increased to 180 (15 blocks of 12 patients) to allow for drop out and screen failures. Sample size will be increased to 180 subjects, this allows for a 20% (n=30) adm/screen fail/etc. error.

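### The protocol states one fixed block length of 12 and nothing keeps it from enrolling staff, so some allocations can be foreseen; sections 3.3 and 4.1 also need a single description of the list

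*Combined protocol and SAP*

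**What the plan says.** Section 4.1 specifies two groups, "a 1:1 treatment to control group ratio", and a list described as "simple randomization block (n=15) design. The total randomization scheme was increased to 180 (15 blocks of 12 patients". One length is given and no variation is mentioned.

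Section 3.3 does not mention blocks. It says "SAS will be used to generate the randomization table using random numbers to determine which treatment subject #1 will receive", continues in the same way for later subjects, and expects the process to finish "resulting in a total of 90 subjects for each treatment group". Randomisation takes place on enrolment. The list is held in the pharmacy, but "access will be granted to Pharmacy and designated research team members". On masking, the section says "Each product will look the same".

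Other sections show where past allocations go:

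- Section 2.3 openly defines Product A as the scented active product and Product B as distilled water.
- Data Collection Form A (Appendix D) and the Demographic/Outcomes Sheet (Appendix H) each have a field for the product, A or B.
- Under section 3.1 the PI/SI collects the completed forms. Under section 3.5 the PI or SI obtains consent.
- On eligibility, the Study Methodology section of the abstract says "The research team member will determine if the patient is eligible for the study".
- Section 2.1 calls the trial single blind without saying who is blinded. Section 10 names one surgical unit as the site.

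**The concern.** In a balanced block of known length, once one arm has used up its share, every remaining allocation in that block is known. Subjects are numbered in order at one site, so a reader of section 4.1 can place the block ends at subjects 12, 24, 36 and so on. The role that receives the forms showing past allocations also consents the next patient, and at least one eligibility criterion, the ability to follow directions, is a matter of judgement.

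If the next arm is foreseen, the decision to approach or accept a patient can come to depend on it. Selection bias of that kind cannot be reliably removed by analysis. Pharmacy custody and identical appearance do not prevent it, because the inference uses past allocations and the block length. It does not require sight of the list.

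Separately, the wording does not settle how the list was made. Section 4.1 calls one design both simple and blocked, and section 3.3 could be read as unrestricted randomisation.

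**Working it through.** **Inputs.** From section 4.1: 15 blocks of 12, generated "using a two-group (treatment vs. placebo") at a 1:1 ratio. From section 3.3: 90 per group. Balance of 6:6 within each block is inferred from these; it is not stated.

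**Step 1, the plan's own figure.** 15 × 12 = 180 and 15 × 6 = 90 per arm. Both reproduce.

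**Step 2, the ceiling.** Assume the boundaries and all earlier allocations in the block are known. After k allocations, one arm is exhausted with probability 2·C(k,6)/C(12,6), where C(12,6) = 924. For k = 6 to 11, C(k,6) is 1, 7, 28, 84, 210 and 462, which sum to 792. The expected number of determined allocations is 2 × 792/924 = 12/7 = 1.71 per block. That is 1.71/12 = 14.3%, or 15 × 1.71 = 25.7 of 180. The last allocation of every block is determined. Two or more are determined in 2 × 210/924 = 45.5% of blocks.

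**Step 3, less complete knowledge.**

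- *Latest allocation unknown.* The k = 11 term drops out: 2 × 330/924 = 0.714 per block, and 0.714/12 = 6.0%.
- *Each earlier allocation known with probability q, independently.* All six allocations of the exhausted arm must be known, so the share is multiplied by q⁶. For q = 0.9, 0.9⁶ = 0.531. For q = 0.8, 0.8⁶ = 0.262.

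| What staff know (boundaries known throughout) | Share certain | Of 180 |
|---|---|---|
| All earlier allocations | 14.3% | 26 |
| 90% of them | 7.6% | 14 |
| All but the latest | 6.0% | 11 |
| 80% of them | 3.7% | 7 |
| 80%, and the latest unknown | 1.6% | 3 |

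Simulation of the 80% row gave 3.8%, which agrees within sampling error. The 80% is an assumption. It borrows the control-group nausea incidence in section 4.1 as a stand-in for the share of patients whose product is used and seen.

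**Step 4, best guess.** Always guessing the arm that is behind in a block of 2m is right with probability [m + (2^(2m)/C(2m,m) − 1)/2]/(2m). For m = 6, 4096/924 = 4.433, and (6 + 3.433/2)/12 = 64.3%, against 50% for unrestricted randomisation.

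**Step 5, varied lengths.** Take blocks of 8, 12 and 16, equally likely, with all earlier allocations and the set of possible lengths known. By simulation, about 1.5 to 1.6% of allocations are certain in advance (about 3 of 180), and the best guess is right about 64% of the time. The first row of the table is the matching figure for the fixed block.

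**The case against.** The strongest reply is that the workflow keeps staff well below the ceiling. Patients are randomised on the day of surgery, and the product is used only if nausea occurs on the unit within 24 hours. A patient without nausea does not reveal the product at the bedside, and the previous patient may still be in theatre when the next one consents. This stands, and it is why the lower rows of the table matter. It is not complete protection: Appendix H also carries a product field, and the documents do not say whether that sheet is left blank for patients without nausea.

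It is also fair to say that 12 is already a fairly long block (a fixed block of 4 gives 33% certain), that varied lengths barely change best-guess accuracy, and that most eligibility criteria are objective. All of this stands. What the change buys is the removal of most certain predictions.

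A further reply is that access to the list is the larger route, since a team member who can open it foresees everything. That is true, but closing that access would leave inference from the block length in place.

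Three stronger readings are tempting and are not supported:

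- *The allocation sequence is published.* Only the block length is. The list is held in the pharmacy.
- *The design uses blocks of 15, which cannot be 1:1.* The next sentence in section 4.1 gives 15 blocks of 12, so 15 is the number of blocks.
- *The trial is simply randomised and will miss 90/90.* Unrestricted randomisation would give exactly 90/90 only 5.9% of the time, but the plan names blocks and 90 per group. Permuted blocks also use random numbers, so section 3.3 can be read consistently with them. The 5.9% describes a design the plan does not use.

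**Conclusion.** The point holds as a modest, cheaply corrected weakness. The plan states one fixed block length, does not withhold it from those who enrol, and routes past A/B codes to the role that takes consent. Up to 14.3% of allocations (about 26 of 180) could be foreseen with certainty. Under partial knowledge that looks more realistic here, the figure is about 2% to 6%.

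The ceiling rests on 6:6 balance, known boundaries and full knowledge of earlier allocations in the block. The lower figures rest on assumed levels of knowledge that the documents do not give. A reader might infer that one allocation in seven will be foreseen, or that enrolment will be steered. The documents show only that the opportunity exists.

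The clash between simple and blocked wording would be clerical on its own, but it should be settled in the same edit.

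**What to change.** - Give one description in sections 3.3 and 4.1: 1:1 permuted blocks with lengths varied at random, generated by someone outside the enrolling team. Lengths of 8, 12 and 16 are one example.
- Delete *simple* and *(n=15)* from section 4.1.
- Keep the block lengths out of the protocol, in a document held by Pharmacy. Varying the lengths is the essential part, because anyone who has read the present text already knows the 12.
- Section 4.1 speaks of the list as already calculated, and the documents do not show whether enrolment has begun. If it has, apply the change to the unused part of the list.

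The cost is re-running one SAS program and editing two sections. The split may no longer be exactly 90/90. With a longest block of 16, the worst case at 180 is a block cut after eight allocations to one arm, a difference of 8 (94/86).

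This does not lower best-guess accuracy, and it does not deal with research-team access to the list, which needs its own correction.

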# 4.2 Method of Data Analysis

Data will be presented as mean ± SD or frequency (percent), where appropriate. Group differences will be compared using Student's t-test, or chi-square tests of association, where appropriate. Data will be assessed for departures from normality with group comparisons adjusted accordingly. The primary hypothesis efficacy endpoint is incidence rate of nausea following surgery. Rates of nausea and 95% confidence intervals will be presented and group comparison will be via chi-square tests. The primary efficacy analysis will only include surgery groups sleeve gastrectomy and Roux-En-Y. However, to expand our knowledge regarding the effect of aromatherapy, we will recruit patients undergoing revisional bariatric surgery but these will only be considered for secondary analyses. As this is an RCT, we anticipate potential cofounders (e.g., gender, type of surgery, etc.) and effect modifiers to be distributed equally. However, in the event of a failed distribution of clinical or demographic characteristics, mixed effects modeling will be substituted to test the primary hypothesis. All analyses will be conducted using SAS (Ver.9.4, Carey, NC) with statistical significance considered as p≤0.05, two-tailed.

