Would you consider using QueaseEASE TM in the	future for nausea?		Yes/No
Would you recommend QueaseEASE™ to family		Yes/No	
Did the participant experience any side effects fro	m the product?		Yes/No
If ves, what side effect (s): Dizziness Lis	htheadedness	Headache	Other

Primary outcome will be an improved patient reported nausea level after receiving the aromatherapy intervention with QueaseEASETM. Secondary outcome will be a decrease in the utilization of antiemetic medication in the first 24 hours in the post-operative bariatric patient population on the surgical unit. Tertiary outcome will be a determination if aromatherapy is more effective for a particular type of bariatric surgery over another (sleeve gastrectomy, Roux-En-Y, revisional bariatric surgery) with post-operative nausea.

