# **Statistical Methodology:**

Data will be presented as mean  $\pm$  SD or frequency (percent), where appropriate. Group differences will be compared using Student's t-test, or chi-square tests of association, where appropriate. Data will be assessed for departures from normality with group comparisons adjusted accordingly. The primary hypothesis efficacy endpoint is the incidence rate of nausea following surgery. Rates of nausea and 95% confidence intervals will be presented and group comparison will be via chi-square tests. The primary efficacy analysis will only include surgery groups sleeve gastrectomy and Roux-En-Y. However, to expand our knowledge regarding the effect of aromatherapy, we will recruit patients undergoing revisional bariatric surgery but these patients will only be considered for secondary analyses. As this is an RCT, we anticipate potential cofounders (e.g., gender, type of surgery, etc.) and effect modifiers to be distributed equally. However, in the event of a failed distribution of clinical or demographic characteristics, mixed effects modeling will be substituted to test the primary hypothesis. All analyses will be conducted using SAS (Ver.9.4, Carey, NC) with statistical significance considered as  $p \le 0.05$ , two-tailed.

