# 3 STUDY METHODS AND PROCEDURES

#### 3.1 Study Treatment/Intervention

Once consent is obtained, the licensed prescriber will enter an order into the patient's electronic medical record (EMR) for the aromatherapy product. It will be a one-time order to administer the aromatherapy product for complaints of nausea while on the surgical unit for the first 24 hours post-operatively. This order will appear on the medication administration record (MAR) in the EMR.

Pharmacy will review and release the aromatherapy order. Pharmacy will be provided with the study Subject Identification (SID) number, a copy of the patient's research consent and randomization scheme generated by SAS which will determine the protocol drug (aromatherapy product A or B). Pharmacy will apply a patient label to study drug and one label on the delivery sheet. The pharmacy will dispense the study drug to the Surgical Unit. The study drug will be placed in the patient's medication bin in the medication room closet to the patient's room. Pharmacy will maintain all delivery sheets in a secure location.

If the enrolled post-operative bariatric patient complains of nausea for first time (initial) while on the surgical unit within the first 24 hours post-operatively, the participant will be offered a one-time aromatherapy intervention with either product A or product B (based on the randomization scheme) for their nausea treatment. A member of the research team will instruct the patient on the use of the QueaseEASETM aromatherapy product (A or B) and also provide them with the educational handout (refer to appendix F: Aromatherapy patient education sheet). The instructions to use are the same for product A as product B.

The direct care nurse will assess the patient's nausea level prior to the intervention. The direct care nurse will provide the patient with their randomized product, and the patient can utilize the product for up to 5 minutes. The nurse will document this one time aromatherapy administration via the MAR. The nurse or a member of the research team will then reassess the patient's nausea level at 5 minutes.

After the aromatherapy intervention the nurse will remove and discard the patient label from the study drug and dispose of the study drug in the appropriate receptacle.

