#### 3.4 Endpoints/Outcomes Measurements

# 3.4.1 Primary outcome.

Primary end-point: Post-operative bariatric patients that use aromatherapy will have a greater decrease in mean nausea levels compared to control group.

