# Data Collection Form A

intervention	
Nausea level before aromatherapy:	0 1 2 3 No Nausea Some Alot Severe
Date:/ Time:	— , s
Administer Aromatherapy product/ Intervent	
Aromatherapy product given:	Product A Product B
Date:/ Time:	— 4
Reassess nausea level after aromatherapy:	
Nausea level 5 minutes after aromatherapy:	0 1 2 3 No Nausea Some Alot Severe
Date:/ Time:	- .a
Did the patient request an antiemetic after the are	omatherany intervention?
YES NO	omaticapy mes content.
Date:// Time:	W4
xx	_ ,
	Add Patient Label

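### The primary endpoint is defined in two incompatible ways, and the one that is sized and tested, incidence of nausea after surgery, cannot respond to the product if read literally

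*Combined protocol and SAP*

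**What the plan says.** **Mean level.** Section 3.4.1 gives the primary endpoint as "Post-operative bariatric patients that use aromatherapy will have a greater decrease in mean nausea levels compared to control group". Hypothesis 1 in the abstract and in 1.2 says the same, and the abstract attaches the 0-3 scale to it. The abstract's Study Methodology puts it a little differently: "Primary outcome will be an improved patient reported nausea level after receiving the aromatherapy intervention".

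**Incidence.** Section 4.2 states "The primary hypothesis efficacy endpoint is incidence rate of nausea following surgery", and the abstract's Statistical Methodology repeats this: "The primary hypothesis efficacy endpoint is the incidence rate of nausea following surgery". Both specify chi-square tests. Section 4.1 plans a Pearson chi-square test and begins its calculation with "Assuming an expected incidence of nausea among controls of 80" percent, a 20% reduction, two-group 1:1 allocation and 90 per group for at least 80% power.

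**When the product is given.** Section 3.3 says "Upon enrollment in the trial, each subject will be randomized to one of two treatment groups". The product itself is offered later and once: "If the enrolled post-operative bariatric patient complains of nausea for first time (initial) while on the surgical unit" is the trigger in 3.1. Section 2.7 makes a current first episode of nausea an inclusion criterion.

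**What is measured.** Form A (Appendix D) records the 0-3 level before the product and one score afterwards, "Nausea level 5 minutes after aromatherapy".

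**The concern.** A change in mean score and a proportion with nausea are different variables, with different tests and different sample-size inputs. An analyst following 3.4.1 and one following 4.2 could report different primary results from the same data, and the plan does not say which governs.

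The second difficulty is timing. The only endpoint with a named test and a sample size concerns whether nausea occurs after surgery, but the product is opened only once nausea has occurred. If that wording is applied as it stands, the primary analysis cannot show benefit even if the product works well.

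**Working it through.** **1. Reproduce the plan's sample size.** Inputs from 4.1 and 4.2: control proportion 0.80, two-sided alpha 0.05, 1:1 allocation. Read the 20% reduction as absolute (0.60), so the average proportion is 0.70.

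n per arm = [1.960 × √(2 × 0.70 × 0.30) + 0.842 × √(0.80 × 0.20 + 0.60 × 0.40)]² / 0.20²
= [1.960 × 0.648 + 0.842 × 0.632]² / 0.04 = 3.249 / 0.04 = 81.2, so 82. With a continuity correction it is 91.

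Power at 90 per arm = Φ[(0.20 − 1.960 × √(0.42/90)) / √(0.40/90)] = Φ(0.992) = 83.9%.

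The claim of at least 80% power therefore reproduces, for a binary endpoint at 80% versus 60%. The trial is sized on the 4.2 endpoint, not the one in 3.4.1.

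**2. Literal incidence.** There are two possible denominators.

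- *Patients given product.* All have already complained of nausea, so incidence is 100% versus 100% and the chi-square statistic is undefined.
- *All randomised patients.* First onset precedes the product, so expected incidence is the same in both arms. The exact rejection probability is the sum of the binomial probabilities of every pair of counts whose Pearson statistic is at least 3.841, with 90 per arm. It is 4.9% at a common incidence of 80% (the figure in 4.1) and 5.0% at one-third (the general figure in 1.3). This is the type I error rate, and it holds whatever the product does.

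**3. Incidence read as any nausea at 5 minutes.** The product could change this. The 75 per arm below is 180 less the 30 losses allowed in 4.1, divided by two. Exact power of the Pearson test:

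| Proportions assumed | 90 per arm | 75 per arm |
|---|---|---|
| 80% vs 60% (20 points absolute) | 84.2% | 76.8% |
| 80% vs 64% (20% relative, 0.80 × 0.80) | 67.3% | 59.1% |

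**4. The 3.4.1 endpoint, mean level.** The documents give no SD and no target difference. Student's t-test appears in 4.2 only as a general method and is not tied to this endpoint. The detectable difference with 80% power is approximately (1.960 + 0.842) × √(2/n) SD, which is 0.418 SD at n = 90; the t-distribution gives 0.420. The SD range of 0.6 to 1.0 points is my assumption, and no gain from baseline adjustment is included.

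| Per arm | Basis | Detectable difference | In points, SD 0.6 to 1.0 |
|---|---|---|---|
| 90 | all randomised | 0.42 SD | 0.25 to 0.42 |
| 75 | after 30 losses | 0.46 SD | 0.28 to 0.46 |
| 72 | 0.80 × 90, if 80% is the share who become nauseated | 0.47 SD | 0.28 to 0.47 |

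These numbers do not remove revisional patients, whom 4.2 excludes from the primary analysis; their expected share is not given. The final analysis set would be smaller still.

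**The case against.** The strongest reply is that nobody intended the literal reading. Section 2.7 requires nausea at entry, yet 4.1 assumes 80% in controls, so 100% versus 100% cannot be what was meant. Form A has a single post-product score, taken at 5 minutes, and labels 0 as no nausea. The natural meaning is a score above 0 at that point, which suits a chi-square test and leaves little to decide after the fact.

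Much of this is fair. The 5-minute reading is plausible, and under it the test is sound. But the plan nowhere adopts it. The 80% could equally be the share of randomised patients who become nauseated, which is what incidence following surgery ordinarily means. It also remains open whether randomised patients who never complain are counted. Most importantly, this reading is still not the 3.4.1 endpoint: a fall from 3 to 1 counts in a mean change and not at all in any-versus-none.

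Three further points stand but do not alter the conclusion. Section 3.4.1 does not itself name the 0-3 scale; the abstract and Form A do. The abstract's improved nausea level could be read as a third, responder-type endpoint, which adds to the ambiguity. The absolute-or-relative question and the loss allowance would matter even with one consistent endpoint, so they should not be counted as evidence of the contradiction.

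**Conclusion.** The concern holds and must be fixed before analysis. The contradiction rests on the text alone and needs no assumption. On the literal wording of 4.2, the primary test has about a 5% chance of rejecting regardless of true effect, against the 80% claimed. On the 5-minute reading, power is about 84% at 90 per arm and 77% at 75, provided that 80% versus 60% is a fair assumption for nausea persisting at 5 minutes, which the plan does not argue. On either reading the stated hypothesis about mean level is unsized. It could be tested with a detectable difference of 0.42 to 0.47 SD at 90 to 72 per arm; what that means in points depends on an SD the documents do not supply.

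**What to change.** Name one primary endpoint, in the same words, in 3.4.1, 4.1, 4.2 and the abstract, taken from the 5-minute score on Form A.

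- **To match the stated hypothesis:** use the 0-3 level 5 minutes after product, compared between arms with adjustment for the pre-product level. The score has only four categories, so an ordinal analysis is a sensible sensitivity check.
- **Analysis set:** randomised patients with a first nausea episode on the unit, within the sleeve and Roux-En-Y restriction already in 4.2.
- **Incidence:** redefine it as the proportion with a score above 0 at 5 minutes, tested by chi-square as a supporting endpoint. Making this the primary endpoint instead would also remove the conflict, but hypothesis 1 and 3.4.1 would then have to be rewritten to match.
- **Section 4.1:** restate it for the endpoint chosen. For the mean level, give the assumed SD and difference, and the number expected to reach product as well as the number randomised. Keep the 80% and 20% figures only if they are justified as proportions still nauseated at 5 minutes, and say whether the 20% is absolute or relative.

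The cost is wording in four places and a revised sample-size statement, which needs a justified SD or 5-minute proportion and may change the required number. Form A already records both scores, so no new data collection is needed.

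### Sections 4.1 and 4.2 do not adjust for the pre-inhaler nausea score on Form A: a missed gain in efficiency, not an error

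*Combined protocol and SAP*

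**What the plan says.** Section 4.1 states for the primary hypothesis that "we will use a Pearson Chi-Square test for proportion difference". Section 4.2 repeats this for the rate ("Rates of nausea and 95% confidence intervals will be presented and group comparison will be via chi-square tests") and names Student's t-test for continuous outcomes, as does the abstract's Statistical Methodology. Section 3.4.1 states the primary endpoint differently: aromatherapy patients "will have a greater decrease in mean nausea levels compared to control group".

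Appendix D, Data Collection Form A, has a field "Nausea level before aromatherapy" scored 0 to 3, and the same scale again 5 minutes after the inhaler. Under sections 2.7 and 3.1 the inhaler is given at a first complaint of nausea, so the first score should be 1, 2 or 3.

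No section names the pre-inhaler score as a covariate or stratum. The only adjustment in 4.2 is a mixed-effects model, substituted if clinical or demographic characteristics turn out unevenly distributed.

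**The concern.** On a four-level scale the starting score limits what can happen next. A patient at 1 can fall by at most 1; a patient at 3 can fall by 3, but must fall by all 3 to be free of nausea. The starting score is therefore a likely predictor of the outcome, and it is already on the form.

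Two things are at stake if it does predict. First, variation in starting severity stays in the error term, which costs precision. Second, a chance excess of severe starters in one arm passes into the treatment estimate. It would raise that arm's residual nausea rate and, where improvement is proportional to the starting level, also raise its mean decrease. One accident of allocation could then make the arm look worse on the 4.2 endpoint and better on the 3.4.1 endpoint.

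There is not much power to spare. Section 4.1 counts an allowance of 30 subjects within the 180; if it is used up, 150 remain, or 75 per arm.

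**Working it through.** **Inputs from the documents.** Section 4.1: "Assuming an expected incidence of nausea among controls of 80%, an alpha level of 5 percent, and a 1:1 treatment to control group ratio"; effect, a "statistically significant 20% reduction in the incidence of nausea among aromatherapy patients"; claim, "90 subjects per group (n= 180 total) provides at least 80% power". Section 4.2: "statistical significance considered as p≤0.05, two-tailed". The text does not say whether the 20% is absolute or relative. The absolute reading, 80% v 60%, is used here because it reproduces the claim.

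**Inputs assumed.** The documents give no distribution of starting scores and no figure for how well they predict the outcome. Starting scores 1/2/3 are taken as 40/40/20%, and predictive strength is varied.

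**Step 1: the plan's own figure.** Power = Φ[(0.20 − 1.96 × SE0) / SE1], where SE0 = √(2 × 0.7 × 0.3 / n) and SE1 = √((0.8 × 0.2 + 0.6 × 0.4) / n).
- n = 90: SE0 = 0.0683, SE1 = 0.0667, power = Φ(0.99) = 83.9%. The claim of at least 80% is met.
- n = 75: SE0 = 0.0748, SE1 = 0.0730, power = Φ(0.73) = 76.7%.
- On the relative reading (80% v 64%), power at 90 per arm is 66.9%. That is a separate matter and does not depend on adjustment.

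**Step 2: rate of nausea.** Simulated trials under a logistic model with overall rates fixed at 80% and 60%, 75 per arm, Pearson chi-square against CMH stratified by starting score:

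| Control rate at score 1/2/3 | Chi-square | CMH | Difference |
|---|---|---|---|
| 80/80/80% (predicts nothing) | 77% | 76% | under 1 point lost |
| 71/83/91% (weak) | 77% | 79% | about +2 |
| 66/86/95% (moderate) | 78% | 82% | about +4 |
| 61/90/98% (strong) | 76% | 85% | about +8 to 9 |

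The chi-square column varies around 76.7% only through simulation error. At 90 per arm the unadjusted test has about 84%, and the weak to strong settings give 86-91%. The top of the range is set by assumption: a still steeper gradient (59/91/99%) gives 77% v 87% at 75 per arm.

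**Step 3: mean decrease, proportional improvement.** Let each point of the starting score persist at 5 minutes with probability q, taken as equal in both arms for simplicity. The mean starting score is 0.4 × 1 + 0.4 × 2 + 0.2 × 3 = 1.8. Its variance is V = 0.4 × 0.8² + 0.4 × 0.2² + 0.2 × 1.2² = 0.56.
- Variance of the change: 1.8q(1 − q) + (1 − q)²V.
- Residual variance after ANCOVA: 1.8q(1 − q).
- q = 0.7: 0.378 + 0.050 = 0.428; reduction 0.050 / 0.428 = 12%.
- q = 0.5: 0.450 + 0.140 = 0.590; reduction 24%.
- q = 0.4: 0.432 + 0.202 = 0.634; reduction 32%.

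Simulations of this model gave reductions of 9-25% and 12-31%, in line with this.

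**Step 4: mean decrease, fixed step.** If every patient improves by the same expected amount whatever the start, the slope of the 5-minute score on the starting score is 1. Subtraction is then already the right adjustment, and the reduction is about nil.

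**Step 5: general check.** With equal pre and post SDs and correlation ρ, the change has variance 2σ²(1 − ρ) and ANCOVA has σ²(1 − ρ²), so the ratio is (1 + ρ)/2. This is 0.60, 0.75 and 0.85 at ρ = 0.2, 0.5 and 0.7. The gain is larger the weaker the correlation, and it does not turn negative in large samples.

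**The case against.** The strongest case against has five parts.

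- **The change score already uses the baseline.** This stands in part. The decrease is pre minus post, so a reader who infers that the t-test ignores the starting score is wrong. What is missing is an estimated slope in place of the fixed value of 1. For the chi-square on rates nothing is used, so there the omission is complete.
- **Nothing in the plan fails.** This stands. Unadjusted tests are valid in a randomized trial, and the stated power is met at 90 per arm. A reader might infer that the trial is underpowered or biased because of this choice; the documents do not support that.
- **The loss is not shown.** This also stands. It is tempting to say that power is thrown away, or that the starting score is the strongest available predictor. The documents establish neither. Appendix H also collects sex, BMI, type and length of surgery and PACU antiemetic use, and nothing ranks these. The cap on improvement bounds the change; for the rate, the argument is only that a higher start lies further from zero, which is plausible but not proven.
- **Section 4.2 has a fallback for imbalance.** It offers some protection against chance imbalance, but it depends on the observed data, has no threshold and does not name this score. It adds no precision when the arms look balanced.
- **The t-test may not be the analysis run.** Section 4.2 adjusts comparisons for departures from normality, which are likely on a four-level scale. The figures in steps 3 to 5 apply to a t-test on change and could differ for a rank test.

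**Conclusion.** The point holds as a missed efficiency that costs little to correct. Neither 4.1 nor 4.2 adjusts for a baseline score recorded for every patient given an inhaler, and the fallback does not fill the gap.

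With starting scores assumed at 40/40/20% and 80% v 60% overall, the effect on the rate comparison at 75 per arm runs from under 1 point of power lost to about 8-9 points gained. For the mean decrease, the variance reduction runs from about nil (fixed-step improvement) to about 10-30% (proportional improvement). These are ranges under assumptions, not estimates for this trial. The omission is certain; the size of the benefit is not. The case for acting rests on the asymmetry: almost nothing to lose, and a plausible gain if the 30-subject allowance is used.

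**What to change.** In 4.1, 4.2 and the abstract's Statistical Methodology, prespecify the following regardless of observed imbalance:

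1. **Mean nausea level:** ANCOVA of the 5-minute score on arm plus the pre-inhaler score, reporting the adjusted mean difference with 95% CI.
2. **Rate of nausea at 5 minutes:** a CMH test stratified by pre-inhaler score, reporting the stratified risk difference with 95% CI.
3. **Population:** state that both apply to randomized patients who received an inhaler for a first nausea episode. Section 3.3 randomizes at enrollment, but under 3.1 the inhaler is given only if nausea occurs, so some randomized patients will have no pre-inhaler score and fit no stratum. If the rate is instead defined over all randomized patients, state how those without an episode are handled, so that the stratified test does not drop them silently.
4. **Supportive analyses:** keep the unadjusted chi-square and t-test.

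Section 4.1 must change along with 4.2, because it names the Pearson test itself. Which of the two analyses is primary depends on reconciling 3.4.1 with 4.2, which should be done first.

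The cost is a few sentences and slightly more analysis work. No new data or patients are needed. If the score predicts nothing, the rate comparison loses under 1 point of power.
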